### 1.2. Benefit/Risk Assessment

This study will be performed exclusively using French national claims database data (SNDS). As a non-interventional study based on secondary use of of medico-administrative data, it meets requirements for a 'European Network of Centers for Pharmacoepidemiology and Pharmacovigilance (EnCEPP) study'. Safety-relevant results will be presented as aggregated data only.

The reader should note that the current knowledge on mepolizumab indicates a list of quite minor side effects (injection site reactions, lower respiratory tract infections, urinary infections, pharyngitis, headache, back pain, and others as mentioned in the Summary of Product Characteristics). Compared with the long-term use of oral corticosteroids (OCS) or short acting beta antagonists (SABA) (currently the most-used anti-asthma medications)(Nwaru et al. 2020), whose side effects include adrenal insufficiency, diabetes, and increased mortality (Zazzali et al. 2015; Sweeney et al. 2016; Barry et al. 2017; Zeiger et al. 2017; Daugherty et al. 2018; Sullivan et al. 2018; Nwaru et al. 2020), mepolizumab initiation is hypothesized to not only decrease the costs associated with recurrent severe asthma, but also costs purportedly due to the comorbid burden associated with rescue medicine.

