## Information available in the SNDS

The available **beneficiary characteristics** include date of birth, gender, area and region of residency, universal medical coverage status, and complementary health insurance status. Chronic diseases are classified according to ICD codes, with registration and end dates, if applicable. For deceased beneficiaries, the date of death is recorded, with the principal, related and associated causes of death.

**Inpatient care** is characterized via linkage with the PMSI database and comports the type of hospital (short-stay care, long-stay care and rehabilitation, psychiatry, or home-hospitalization), within-hospital trajectories (for example, passages through emergency departments or intensive care), principal and secondary diagnoses associated with hospital entry, the procedures performed during each stay, the consumption of a special drug category termed "costly drugs", entry and leave dates and associated mode (transfer, return home), and cost information.

**Outpatient care** comprises care not affected to a hospital stay and the related data include drug delivery (international non-proprietary name and anatomical therapeutic chemical classification, packaging identifier code, the common dispensing unit, quantity and date of delivery), medical devices (type, quantity and date of delivery), medical visits (date and speciality of the physician),

paramedical visits (date and type (nursing, physical therapy, etc)), medical procedures (date and type), lab tests (date and type), government benefits (beginning and end dates and type (disability, maternity, sick leave, etc), medical transportation usage. Each outpatient care element is further characterized according to professional source and legal status (pharmacy, specialist, nurse, therapist, etc), the area and region of residency, the price presented for reimbursement and the amount actually reimbursed by the single payer system.

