### Diagnoses / Comorbidities

Resource-use algorithms will be developed as indicators of severe asthma (via a combination of specific asthma controllers and oral corticosteroids), uncontrolled asthma (combinations of oral corticosteroids, hospitalization for asthma, specialist and/or emergency care usage), chronic obstructive pulmonary disease and diabetes (specific drug deliveries). Evidence of further comorbidities will be collected (via a specific list of long-term diseases, and via the primary and secondary coding performed during hospitalizations) and their incidence before versus after T0 studied.

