# 3. Study Design

## 3.1. Overall Design

This retrospective, non-interventional (not involving human subjects) database study will compare real-life patient health resource consumption before versus after a first injection of mepolizumab. Data concerning patients receiving mepolizumab will be collated for a 12-month period (the "baseline period") preceding a first index treatment (at "T0") and compared to a 12-month period occurring after the index treatment (the "exposure period")(Figure 5-1).

[figure not shown]

Figure 3-1 Graphic presentation of the basic study design comparing health care resource use data between a one-year baseline period and a one-year exposure period after the first administration of mepolizumab (T0).

The expected correspondence to calendar time (Figure 5-2) is an inclusion period for T0 starting in February 2018 to December 2018, with 12 months of "follow-up" corresponding to the year 2019. It follows that baseline data will reach back to February 2017. If data for exposure periods longer than 12 months are available, these will also be collected to describe future trajectories of health resource use in as much as possible.

Figure 3-2 The expected correspondence with real time is an inclusion period covering patients who started mepolizumab in the year 2018, with 12 months of "follow-up" in the year 2019.

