### 4.2. Exclusion Criteria

- Health resource use data covering the 12 months preceding the first filled prescription for mepolizumab are not available
- Health resource use data covering the time period starting at the first filled prescription for mepolizumab and ending at subsequent death or at 12 months later are not available

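### The before/after comparison of comorbidity incidence has no look-back before the baseline year, so a first-record count of hospital-coded chronic conditions would be biased towards a fall

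*Protocol*

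**What the plan says.** Section 2, Diagnoses / Comorbidities, has two parts. The first develops resource-use indicators for severe asthma, uncontrolled asthma, COPD and diabetes; COPD and diabetes rest on drug deliveries. The second part reads "Evidence of further comorbidities will be collected (via a specific list of long-term diseases", followed by "via the primary and secondary coding performed during hospitalizations) and their incidence before versus after T0 studied". The incidence comparison therefore draws on two sources, long-term disease listings and hospital coding.

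The two sources differ in what they date. On the first, section 2 (Information available in the SNDS) states: "Chronic diseases are classified according to ICD codes, with registration and end dates, if applicable". It describes no onset date for hospital diagnoses.

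The data window is set in section 3.1. Data are collated for 12 months before T0, with "an inclusion period for T0 starting in February 2018 to December 2018", and then: "It follows that baseline data will reach back to February 2017". Section 4.2 excludes a patient only if "Health resource use data covering the 12 months preceding the first filled prescription for mepolizumab are not available". Section 3.1 allows data beyond 12 months after T0 to be collected, but makes no such allowance before the baseline year. The protocol does not define a new case, set a washout or exclude prevalent disease.

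**The concern.** Incidence counts new cases, so it needs a way to recognise old ones. For a chronic condition known only from a discharge code, that way is earlier history. The baseline year has none, or at most a few months for late starters. The exposure year always has at least the 12 baseline months behind it.

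Under a first-record count, this difference moves cases in one direction. A patient with long-standing disease who is first coded in the baseline year counts as new there and cannot count again after T0. The after/before ratio then falls below 1 even if nothing has changed.

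The direction matters. Section 1.2 hypothesises that starting mepolizumab will lower asthma costs and also "costs purportedly due to the comorbid burden associated with rescue medicine". A reader who holds that hypothesis could take an artefactual fall in comorbidity as support for it.

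**Working it through.** **Inputs from the protocol.** Expected N is 29 × 97 = 2813 (section 8.1), which reproduces. Pre-T0 data cover 12 months. If extraction starts in February 2017 for everyone, a December 2018 starter has about 22 months, that is up to 10 months before the baseline year. The protocol gives no figure for comorbidity incidence, so there is none to reproduce.

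**Assumed inputs.** These are prevalence p at the start of the baseline year, the yearly chance that a prevalent condition is coded (c or q), and true yearly onset i, equal in both years. There is no treatment effect, so the correct ratio is 1.00.

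**Model A: every case, old or new, is coded with probability c per year; first record = new case; no look-back.**
- Baseline = p·c + (1−p)·i·c
- Exposure = p·(1−c)·c + (1−p)·i·c + (1−p)·i·(1−c)·c. The last term is baseline-year onset first coded after T0.

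With i = 1%:

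| p | c | Baseline | Exposure | Ratio |
|---|---|---|---|---|
| 0.05 | 0.3 | 0.0150 + 0.00285 = 0.01785 | 0.0105 + 0.00285 + 0.0020 = 0.0153 | 0.86 |
| 0.15 | 0.7 | 0.1050 + 0.00595 = 0.11095 | 0.0315 + 0.00595 + 0.0018 = 0.0392 | 0.35 |

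In 2813 patients these are about 50 v 43 and 312 v 110 apparent new cases.

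**Model B: onset is coded at once, old disease is coded with probability q per year, and all of L years of earlier data are used.**
- Baseline = p·q·(1−q)^L + i
- Exposure = p·q·(1−q)^(L+1) + i

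With L = 0, p from 5% to 30%, q from 0.2 to 1.0 and i of 1% or 3%, the ratio is below 1 in every scenario. It runs from 0.95 (p = 5%, q = 0.2, i = 3%: 0.040 v 0.038) to 0.03 (p = 30%, q = 1.0, i = 1%: 0.310 v 0.010).

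Middle case (p = 15%, q = 0.5, i = 1%): 0.085 v 0.0475, ratio 0.56, or about 239 v 134 cases. The two groups are disjoint, so a paired comparison gives z = (239 − 134)/√(239 + 134) ≈ 5.4, with no true change. In Model A's mild case, z = (50 − 43)/√(50 + 43) ≈ 0.7, so the artefact would not reach significance.

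**Extra history used unequally does not cure it.** In the same middle case:
- L = 2: baseline 0.15 × 0.5 × 0.25 + 0.01 = 0.0288; exposure 0.15 × 0.5 × 0.125 + 0.01 = 0.0194; ratio 0.67.
- L = 3: 0.0194 v 0.0147; ratio 0.76.

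**Equal look-back does.** With a fixed window of W years before each period and steady prevalence, both rates equal p·q·(1−q)^W + i. For W = 2 that is 0.0288 in each year, ratio 1.00.

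**Other definitions.**
- If onset is dated by registration, the ratio is 1.00.
- If incidence means any record in the period, baseline = p·q + i = 0.085 and exposure = (p + i)·q + i = 0.090. The ratio is 1.06 (1.14 with i = 3%), so there is no built-in fall.

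**The case against.** The strongest objection is that the protocol never says a first record is a new case. The word incidence is undefined, neighbouring endpoints in section 2 are counts per period, and a definition can properly sit in an analysis plan, which is not at hand. A reader might infer that comorbidity incidence must fall by construction. The documents do not support that: the fall depends on a first-record count and disappears under an any-record count. What remains is that an any-record count is period prevalence, so the label would then be wrong. An analysis plan also cannot recover history that was never requested. Appendix 3 (Data Management) requires the selection algorithm and variable list before access.

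The scope is narrow. Long-term diseases carry registration dates, so earlier onset can be recognised for that source. A reader might extend the point to diabetes, COPD or osteoporosis. But diabetes and COPD are drug-delivery indicators in the preceding sentence and not clearly part of the incidence clause, and section 2 names osteoporosis under costs.

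The link to the hypothesis is also limited. Section 1.2 speaks of costs, not of incidence, and comorbidity incidence appears nowhere in the objectives and endpoints table. A false benefit is a risk of interpretation, not something the protocol sets out to claim.

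Finally, 12 months is a minimum for eligibility, and late starters may have up to about 22. That holds, but look-back would then vary with T0 date and the exposure year would still have more history behind it than the baseline year.

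**Conclusion.** The point holds for chronic conditions identified from hospital coding and counted by first record. The comparison then favours a fall because the two periods have unequal history. The protocol fixes a window that leaves no sound alternative for counting new cases from this source.

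The size rests wholly on assumed inputs. The ratio is 0.35 to 0.86 for prevalence 5-15%, coding probability 0.3-0.7 and 1% onset, and 0.03 to 0.95 over the wider range. At the mild end the artefact would go unnoticed; in the middle case it would look highly significant. The false discovery rate correction in section 8.3.2 addresses multiplicity and would not remove this bias.

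This concerns one descriptive outcome. The primary total-cost endpoint is untouched. It is worth correcting because the remedy depends on what data are requested.

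**What to change.** In section 2, Diagnoses / Comorbidities:
- Date onset by long-term-illness registration wherever it exists.
- For hospital-coded chronic conditions, extend the data request before the baseline year. Count a new case only if there is no record in a look-back of the same fixed length (for example 24 months) before each period. Equal length is essential; using all available history would leave the imbalance.
- State that equal look-back balances the two periods but does not clear out all old disease. In the middle case, 0.0188 of the 0.0288 is still prevalent disease, so levels are overstated in both years.
- If earlier data cannot be obtained, replace incidence with the proportion having any record in each period, call it period prevalence, and do not interpret it as new onset. It may rise slightly with no treatment effect.

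The cost is a somewhat wider SNDS extraction and slightly more analysis work. Section 1.3 says identifiers are lifelong but that not all stored data are immediately accessible, so availability should be confirmed. The study calendar places authorisations in April-June 2020 and extraction in July-September 2020, so the change belongs in the protocol before the request is settled.

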#### Costs

Cumulative per-beneficiary costs (including all health care resource uses and government benefits) will be described and contrasted between the baseline and exposure periods. This will be performed at several levels: (i) all costs regardless of source or potential link with diagnoses, (ii) costs due to mepolizumab, (iii) costs that can be associated with asthma-specific care, (iv) costs that can be associated with the monitoring and care for certain key comorbidities (diabetes, bone density/osteoporosis).

### Subpopulations of interest

Sub populations of interest and subject to comparative analyses include sex, age groups, beneficiaries with versus without indicators of severe asthma, uncontrolled asthma, chronic obstructive pulmonary disease, and diabetes (identified via the prescription of specific drugs, hospitalization diagnoses, assessments or combinations thereof).

Objectives	Endpoints
Primary	
To estimate the change in associated costs for the first year of treatment	
 
Total health care costs for the year preceding the initiation of mepolizumab, as well as for the year after.
 

Secondary	
To describe the initial one-year changes in health resource use before and after the initiation of mepolizumab treatment	
 
Cumulative estimates for health resource use and associated costs for the year preceding the initiation of mepolizumab, as well as for the year after.
 

Tertiary/Exploratory	
To further characterize rates of change in health resource usage and/or costs in subpopulations of interest	
 
Sub populations of interest and subject to comparative analyses include sex, age groups, beneficiaries with versus without indicators of severe asthma, uncontrolled asthma, chronic obstructive pulmonary disease, and diabetes (identified via the prescription of specific drugs or combinations thereof).
 

# 3. Study Design

## 3.1. Overall Design

This retrospective, non-interventional (not involving human subjects) database study will compare real-life patient health resource consumption before versus after a first injection of mepolizumab. Data concerning patients receiving mepolizumab will be collated for a 12-month period (the "baseline period") preceding a first index treatment (at "T0") and compared to a 12-month period occurring after the index treatment (the "exposure period")(Figure 5-1).

[figure not shown]

Figure 3-1 Graphic presentation of the basic study design comparing health care resource use data between a one-year baseline period and a one-year exposure period after the first administration of mepolizumab (T0).

The expected correspondence to calendar time (Figure 5-2) is an inclusion period for T0 starting in February 2018 to December 2018, with 12 months of "follow-up" corresponding to the year 2019. It follows that baseline data will reach back to February 2017. If data for exposure periods longer than 12 months are available, these will also be collected to describe future trajectories of health resource use in as much as possible.

Figure 3-2 The expected correspondence with real time is an inclusion period covering patients who started mepolizumab in the year 2018, with 12 months of "follow-up" in the year 2019.

# 3.2. Participant and Study Completion

This study is primarily descriptive and the identification of beneficiaries receiving mepolizumab will be exhaustive. In this context, traditional sample size calculations are inappropriate/unnecessary. A first estimate indicates an expected sample size of 2813 patients (see section 10.1)

As concerns exclusion from the analysis due to missing data, we expect this to be minimal as the databases are exhaustive and obligatory concerning drug dispensations.

# 3.3. End of Study Definition

Patients will be identified as beneficiaries within the French National Health Data System [Système National des Données de Santé](SNDS), which covers approximately 66.6 million people, or 99% of the French population (Bezin et al. 2017). Longitudinal coverage of a given beneficiary stops at death or at when he/she moves abroad (De Roquefeuil et al. 2009).

# Study calendar

PROPOSAL SUBMISSION:	25 November 2019
PROPOSAL OF INTEREST COMMUNICATED BY GSK:	20 January 2020
FIRST DRAFT OF PROTOCOL REQUESTED BY GSK:	29 February 2020
AUTHORIZATIONS/APPROVALS:	April-June 2020
PUBLIC DISCLOSURE/REGISTRATIONS:	May-June 2020 (This is flexible, but must be performed right before data extraction)
DATA EXTRACTION AND WRANGLING:	July-September 2020
ARTICLE WRITING:	February 2020 to November 2020
FIRST SUBMISSION OF ARTICLE:	December 2020

RESULTS REPORTING ON CLINICALTRIALS.GOV:	July-September 2021 (Can be performed
	earlier, as soon as the princeps article is
	accepted).

# 3.4. Scientific Rationale for Study Design

Our goal is to use real-life, exhaustive data to describe 1-year changes in health resource use before and after the initiation of mepolizumab treatment among beneficiaries of the French health insurance program. This goal necessitates the use of the SNDS databases (SNIRRAM, PMSI, BMCD).

#### 3.5. Justification for Dose

Not applicable.

# 4. Study Population

The study population will comport all beneficiaries in the national French SNDS database who were prescribed mepolizumab and for whom health resource use data is available for the 12 months preceding and following a first filled prescription for mepolizumab.

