# 2. Objectives and Endpoints

In light of the clearly documented clinical efficacy of mepolizumab for the treatment of asthma, our hypothesis is that mepolizumab treatment results in decreased consumption of health care resources, with corresponding decreases in overall costs for the single payer social security health insurance program in France.

The overall objectives of this study are: (i) using the SNDS French national database, to identify a representative, nation-wide population of patients treated with mepolizumab with a follow-up period of at least 12 months, (ii) to describe the initial one-year changes in health resource use before and after the initiation of mepolizumab treatment and (iii) to estimate the change in associated costs for the first year of treatment. These initial data will additionally serve as a basis for the design of longer-term studies.

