## 6.3. Lost to Follow Up

Not applicable to the present database study.

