# 8.3. Statistical Analyses

### **8.3.1.** General considerations

Children and adult patient data will be analyzed (no age limits will be imposed).

Descriptive statistics for quantitative variables will include sample size and number of missing values, range, median (interquartile range), and mean ± standard deviation. Summary statistics for qualitative variables will include sample size and number of missing values, the frequency and percentage (over non-missing values unless otherwise specified) for each category. All applicable statistical tests will be performed using a bilateral 5% significance level. All confidence intervals (CI) presented will be 95% and two-sided.

The lost to follow-up patients (e.g. exit from one of the insurance schemes available in the SNDS, expatriation with exit from French insurance schemes) will not be included in the study. No replacement of missing values will be performed. For a given patient with a complete follow-up period, all reimbursed healthcare consumptions are reported in the database.

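### The protocol gives two incompatible rules for patients who die within 12 months of T0: Section 4 removes them, Section 4.2 keeps them

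*Protocol*

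**What the plan says.** Four places in the protocol bear on who needs how much data after T0.

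- Section 4 (Study Population) takes beneficiaries "for whom health resource use data is available for the 12 months preceding and following a first filled prescription for mepolizumab". It makes no exception for death.
- Section 2 (Objectives and Endpoints) aims at "patients treated with mepolizumab with a follow-up period of at least 12 months".
- Section 8.1 (Sample Size Determination) describes the roughly 2,813 patients as having one year of follow-up.
- Section 4.2 (Exclusion Criteria) removes a patient only if data for the period "ending at subsequent death or at 12 months later are not available".

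Section 3.3 supplies the link between them: "Longitudinal coverage of a given beneficiary stops at death or at when he/she moves abroad".

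The primary endpoint (table at the end of Section 2) is total health care cost in the year before and the year after initiation. Section 8.3.2 compares the two periods with paired t-tests or paired Wilcoxon tests. Neither place says how a year cut short by death is entered.

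**The concern.** Every patient is alive throughout the baseline year by construction, so death can occur only in the exposure year. The rule for deaths therefore acts on one side of the paired comparison only.

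If decedents are dropped, the cohort is selected on an outcome that follows T0. Costs run up before death leave the exposure year, and the cohort no longer matches the aim in Section 2 of a representative national population. If decedents are kept, those costs are counted, but their use of drugs, consultations and hospital days stops at death. Without a caution, a reader may take that as reduced need.

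Either choice can favour the study's hypothesis of lower consumption. Two analysts working faithfully from this protocol could build different primary cohorts, so the rule should be settled before any result is seen.

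**Working it through.** **The sections side by side, for a patient with a full baseline year**

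| Event after T0 | Sections 2, 4, 8.1 (with 3.3) | Section 4.2 | Section 8.3.1 |
|---|---|---|---|
| Dies at month 6, data complete to death | Out: no 12 months of data | In | Not mentioned |
| Leaves the insurance schemes at month 6 | Out | Out | Out |

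The conflict is confined to the first row.

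**The plan's own figures**

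Expected N (Section 8.1): 29 x 97 = 2,813, as stated.

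Power at d = 0.063, two-sided 5%, normal approximation Phi(d x sqrt(n) - 1.960):

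- Paired t-test: 0.063 x sqrt(2,813) = 3.341; 3.341 - 1.960 = 1.381; power 91.6%.
- Paired Wilcoxon, effective n = 2,813 x 3/pi = 2,686: 0.063 x sqrt(2,686) = 3.265; 3.265 - 1.960 = 1.305; power 90.4%.

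The stated 90% or better reproduces.

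**Patients affected** (12-month mortality m is an assumption; the documents give none)

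- m = 1%: 2,813 x 0.01 = 28
- m = 2%: 2,813 x 0.02 = 56
- m = 5%: 2,813 x 0.05 = 141

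**Power if they are dropped**

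At m = 5%, n = 2,813 - 141 = 2,672. Power at d = 0.063 is 90.2% (t-test) or 88.9% (Wilcoxon). The losses are 91.6 - 90.2 = 1.4 and 90.4 - 88.9 = 1.5 points.

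**Shift in the primary estimate**

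Let D be the amount by which a decedent's year-after minus year-before cost differs on average from a survivor's. Then mean(all) - mean(survivors) = m x D. With D assumed at EUR 20,000-40,000:

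| m | D = EUR 20,000 | D = EUR 40,000 |
|---|---|---|
| 1% | 200 | 400 |
| 2% | 400 | 800 |
| 5% | 1,000 | 2,000 |

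**Relative form, which needs no euro figure**

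If a decedent's exposure-year cost is k times a survivor's, the mean exposure-year cost differs between the two rules by m x (k - 1):

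- m = 1%, k = 2: +1%
- m = 5%, k = 0.5: -2.5%
- m = 5%, k = 5: +20%

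The sign depends on whether high cost before death or early cessation of cost dominates.

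**The case against.** The best defence is that the operative text already keeps decedents. Section 8.2 analyses everything included and not excluded, which points to the criteria in Sections 4.1 and 4.2. Section 4.2 is the only criterion that mentions death, and a specific criterion normally outranks an introductory sentence, an objective or a sample-size aim. This makes Section 4.2 the likelier intention. It does not remove the conflict: Section 4 is itself the definition of the population, two other sections agree with it, and nothing says which governs.

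A second defence is that a decedent's year-after total is complete, because cost after death is a known zero. This stands. A reader might infer that keeping decedents makes the paired tests invalid because the periods are unequal. The endpoint is a one-year total, not a rate, so the paired comparison remains valid once the convention is stated.

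A reader might also infer that the protocol has a third rule, or that it contradicts itself on patients who leave coverage. It does not. Section 8.3.1 says that patients lost through, for example, "expatriation with exit from French insurance schemes) will not be included in the study", and it does not mention death. Sections 4 and 4.2 exclude the same leavers for lack of data. Section 6.3 ("Not applicable to the present database study") sets no competing rule. Excluding leavers does use information from after T0, but it is stated consistently. Keeping them as censored and reading the primary result from the mean cumulative function would need independent censoring and would replace the planned paired comparison. Section 8.3.3 offers the function of differences only as something that can be computed.

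Finally, the size rests on assumed inputs, and the study calls itself primarily descriptive. Both points are fair. They limit what can be said about magnitude, not about the contradiction.

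**Conclusion.** The point holds for deaths within 12 months of T0. Sections 2, 4 and 8.1, read with Section 3.3, remove these patients; Section 4.2 keeps them. The first reading conditions the primary cost comparison on surviving the exposure year. The contradiction follows from the text alone and needs no assumption.

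Its size is uncertain because it depends wholly on mortality and cost inputs that the documents do not give. Over the ranges assumed above, the effect on the mean difference could be negligible or material. The loss of power is minor: what changes is the population and the estimate, not the ability to detect a difference.

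**What to change.** 1. In Sections 2, 4 and 8.1, qualify the 12-month requirement so that it ends at death if death comes first, in line with Section 4.2. Initiators with 12 months of baseline data who die in year 1 are then analysed.
2. In Section 8.3.2, state that a decedent's year-after total is cost to death and zero afterwards, and that this total enters the paired comparison.
3. State that lower resource use after death is not to be read as reduced need.
4. Report the same comparison in 12-month survivors as a sensitivity analysis, with the number of deaths.
5. Leave the exclusion of leavers as it is, and report how many were excluded.

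The cost is a few sentences and one additional run. Section 2 lists date of death among the available beneficiary data, and the patient-selection algorithm in Section 8.1 rests on medication codes, so no new data are needed.
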